5. TRIAL MEASUREMENTS

5.1. EFFICACY

Total joules provided during a patient encounter will be measured. First shock success percentage will be compared between groups. Transthoracic impedance with each shock (a measurement provided by the defibrillator) will also be recorded.

5.2. SAFETY AND TOLERABILITY

Safety will be assessed by recording of AEs, and MACCE.

- Participants will be questioned and monitored throughout in-patient stay with regard to any AEs they may have experienced. See Section 6 for further details on recording AEs.
- Vital signs will be measured after the participant has been supine for 5 minutes and will include blood pressure (BP), pulse rate, respiratory rate and temperature.
- Measurement of chest pain 30 minutes post procedure will be elicited by medical staff (Ordinal scale of 0-10).
- Shock provided to proceduralist will be documented.

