Cardiology Department, HNELHD
Clinical Trial Protocol: PRESSURE-AF

Version: 1.4
Date: 24/11/2020

Study Title:	Investigating the Efficacy of Chest Pressure for Direct Current Cardioversion in Atrial Fibrillation: A Randomised Control Trial (Pressure-AF)
Protocol Number:	2020/ETH02116
CTN Number:	ACTRN12620001028998p
Intervention	Chest Pressure
Indication:	Direct Current Cardioversion for Atrial Fibrillation
Study Design:	Investigator-initiated
Version:	1.4
Date:	24th November 2020

CONFIDENTIAL

Cardiology Department, HNELHD
Clinical Trial Protocol: PRESSURE-AF

Version: 1.4
Date: 24/11/2020

PROTOCOL SYNOPSIS

Study Title:	Investigating the Efficacy of Chest Pressure for Direct Current Cardioversion in Atrial Fibrillation: A Randomised Control Trial (Pressure-AF)
Study Period:	2021-2023
Hypothesis	The routine use of manual chest pressure for direct current cardioversion in atrial fibrillation will result in decreased energy requirements and will prove safe for patient and proceduralist.
Objectives:	
Primary objective:
 
• To assess the efficacy of chest pressure for direct current cardioversion in atrial fibrillation. 
The secondary objectives are:
 
• To confirm safety and tolerability of chest pressure for patient and proceduralist
Study Plan	
This is a multi-centre, randomised, single blinded trial of chest pressure for direct current cardioversion in atrial fibrillation.
 
Participants will be screened from all participants referred for cardioversion for atrial fibrillation aged over 18 years of age. Randomisation will occur after consent is obtained and on enrolment into the study.
 
Participants will be randomised to an initial strategy of chest pressure (intervention) or a strategy of chest pressure only if refractory to cardioversion without pressure (control).

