2.7.3. Chest pressure standardisation

The application of standardised chest pressure is needed to ensure consistency of the intervention. A review of chest pressure provided by Cardiology Advanced Trainees (the proceduralists for the intervention) was performed. Of thirty-six measurements, on a single set of scales, between four advanced trainees (8 measurements each), an average of 25.5±2.6 kilograms of chest pressure was provided.

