2.7.5. Method of assigning participants to treatment group

Participant eligibility will be established before randomisation. Eligible participants who consent to involvement will be assigned to either the control or intervention arm in a 1:1 ratio. Patients will be

Cardiology Department, HNELHD
Clinical Trial Protocol: PRESSURE-AF

Version: 1.4
Date: 24/11/2020

randomised via a randomisation app. This app, given to all researchers, will provide synchronised information about patient allocations.

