3.2. DAY OF CARDIOVERSION

On the day of cardioversion the following will be performed:

- Review eligibility criteria.
- Record participant medical history and medications.
- Record the height and weight of the patient.
- Vital signs (see Section 5.2).
- 12-lead ECG.
- Written informed consent.
- Upon confirmation of eligibility and consent to proceed, participants will be randomised.

The protocol for DC cardioversion (control or intervention) will then be performed based on randomisation. After the DC cardioversion is completed, the following will be performed:

- Chest pain 30 minutes post procedure will be recorded (0-10 ordinal scale)
- Record of post-procedural complications:
 - shock provided to proceduralist

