4.2. SAFETY AND TOLERABILITY ENDPOINTS

- Chest pain 30 minutes post procedure.
- Shock to proceduralist

Cardiology Department, HNELHD
Clinical Trial Protocol: PRESSURE-AF

Version: 1.4
Date: 24/11/2020

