8.6.2. Other safety measures

Continuous variables will be summarised along with the change from baseline at each time point by treatment group. Other variables will be summarised as appropriate to the data.

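### The 30-minute chest pain score is elicited by medical staff, with no requirement that they be unaware of the arm or different from the operator

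*Protocol*

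**What the plan says.** The synopsis (Study Plan) describes the blinding in one line: "This is a multi-centre, randomised, single blinded trial of chest pressure for direct current cardioversion in atrial fibrillation". It does not say who is blinded, and the overall design statement in section 2.3 does not mention blinding.

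Section 4.2 lists two safety and tolerability endpoints: "Chest pain 30 minutes post procedure" and "Shock to proceduralist". The first concerns the patient and the second the operator.

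Two places describe how pain is collected. Section 3.2 says "Chest pain 30 minutes post procedure will be recorded (0-10 ordinal scale" and names no recorder. Section 5.2 does name one: "Measurement of chest pain 30 minutes post procedure will be elicited by medical staff (Ordinal scale of 0-10".

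Two further passages bear on who knows the arm. Section 2.7.3 identifies the operators: "A review of chest pressure provided by Cardiology Advanced Trainees (the proceduralists for the intervention) was performed". Section 2.7.5 says of the randomisation app: "This app, given to all researchers, will provide synchronised information about patient allocations".

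The synopsis (Statistical Analyses) puts post-procedure chest pain among the secondary endpoints to be analysed by the methods given for the primary endpoint, with two-tailed tests at the 5% level.

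**The concern.** A 0-10 pain score can be moved by how the question is put and by who puts it. The other listed endpoints (joules delivered, rhythm, impedance, a shock to the operator) depend much less on that. Here the person applying the intervention cannot be blinded, and the protocol lets that person, or a colleague who knows the arm, obtain the score. The participant has recently been sedated with propofol, with or without midazolam.

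What is at stake is how the pain comparison can be read. Section 1.1 names lower pain after the procedure as a possible benefit of pressure, and the synopsis makes tolerability for the patient part of the secondary objective. If questioners who know the arm expect pressure to hurt more, or to hurt less because fewer shocks are needed, part of an observed difference could come from the questioning, or a real difference could be masked. A bias that enters at collection cannot be removed by any later analysis plan.

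**Working it through.** No arithmetic settles this point, so the check sets the passages side by side.

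1. **Who can be blinded?** The operator applies the pressure and so knows the arm. The participant is under intravenous sedation in both arms (sections 2.7.1 and 2.7.2), so participant blinding is feasible. It is the natural reading of a single-blind design, but it is inferred.

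2. **Who obtains the score?** Section 5.2 gives medical staff, and section 3.2 gives nobody. Neither section adds a condition on knowledge of allocation or on attendance at the procedure.

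3. **Does that description include people who know the arm?** Yes. Cardiology advanced trainees are medical staff and are the operators (section 2.7.3). On its plain wording, section 2.7.5 also makes allocations available to every researcher holding the app. Absence from the room is therefore not enough to keep a researcher unaware of the arm.

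4. **Is there a safeguard elsewhere?** The only other blinding provision is the blinded data review that decides exclusions from the per-protocol set (synopsis and section 8.3). It takes place after the data are collected and does not cover how an outcome is assessed.

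5. **Is the endpoint compared between arms?** Yes, by the synopsis.

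6. **Does the point reach the primary result?** No. The plan's one sample-size figure concerns total joules. The normal-approximation formula is n per arm = 2 × (1.960 + 0.842)² × (SD/difference)². With SD 188 J and difference 60 J this is 2 × 7.85 × 9.82 ≈ 154.1, or 155 rounded up. That gives 310 in total against the stated 308, so the figure reproduces. Pain plays no part in it.

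7. **Can the bias be sized?** No. The protocol gives no mean, standard deviation or expected difference for pain, and nothing from which an interviewer effect could be derived.

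**The case against.** The strongest reply is that this is an unspecified role and not a wrong design. No passage says that the operator, or anyone who was in the room, asks the question. Nor does the protocol say that whoever asks is a researcher holding the app. The answer is the patient's own number, and if the patient is blind, the patient's own expectation remains controlled. All of this stands. It limits the point to interviewer influence, recording and disclosure. It does not remove it, because section 5.2 does assign the task, and it assigns it to a group that includes the operators without any condition.

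A reader might be tempted by stronger readings that the documents do not support:

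- **That the participant's blinding achieves nothing for pain.** It still protects a self-reported answer in part.
- **That pain is the only subjective patient information.** Adverse events are also elicited by questioning (sections 5.2 and 6.3) and graded by their effect on daily routine (section 6.1).
- **That a baseline pain score is required but never collected.** Section 8.6.2 says "Continuous variables will be summarised along with the change from baseline at each time point by treatment group". That applies to continuous variables, while the protocol calls the pain scale ordinal. The next sentence of 8.6.2 leaves other variables to be summarised as suits the data, and a randomised comparison at 30 minutes needs no baseline.
- **That the pain comparison would be uninterpretable.** An unspecified questioner creates a risk of bias but does not demonstrate any.

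Patient tolerability appears as an objective only in the synopsis; section 2.2 names the proceduralist alone. Pain is nevertheless a listed endpoint in both places.

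**Conclusion.** The concern holds in a limited form. The protocol gives the only patient item among its listed safety and tolerability endpoints to staff who may know the arm, with no condition that would keep them unaware of it. The score is left exposed to interviewer influence, recording bias and disclosure of allocation, with partial protection if the participant is the blinded party.

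The size and direction of any bias are unknown and cannot be estimated from the documents. The conclusion rests on two readings: that single blinded refers to the participant, and that medical staff carries its ordinary meaning and so includes the operators. The matter is confined to one tolerability endpoint. It is worth correcting because the remedy is cheap and the problem cannot be repaired after collection.

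**What to change.** - **Synopsis and section 2.3:** state that the participant is the blinded party.
- **Sections 3.2 and 5.2:** have the participant complete the 0-10 scale on a card at 30 minutes, before being told the allocation or the number of shocks. Existing staff who did not attend the procedure and do not consult the allocation app hand over and collect the card. The operator and others who were present do not ask for the score.

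The cost is a printed card and a few sentences, with no extra visit or assessment. It assumes that each site has someone on hand who was not at the procedure; the protocol does not describe recovery staffing, so sites should confirm this. The small downside is an occasional missing card when a participant is still drowsy at 30 minutes. Section 7 already requires assessments not done to be marked in the case report form, so such gaps would be visible.

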6. ADVERSE EVENTS

The definitions of AEs and SAEs are given below. It is extremely important that all staff involved in the trial are familiar with the content of this section. The PI is responsible for ensuring this.

6.1. ADVERSE EVENT DEFINITIONS

An AE is defined as any untoward medical occurrence in a participant or clinical investigation participant administered the study treatment and which does not necessarily have a causal relationship with this strategy. An AE can therefore be any unfavourable and unintended sign (including an abnormal laboratory finding), symptom, or disease temporally associated with the use of a medicinal (investigational) product whether or not related to the medicinal (investigational) product.

Laboratory reference ranges are defined by upper or lower limits of parameters of the laboratory. The Investigator should ensure that each parameter out of the normal range is assessed for clinical significance and potential for being an AE. It is at the discretion of the Investigator to document any change in laboratory result as an AE if he considers the change to be clinically significant, even if the absolute value is within the alert limit or reference range.

The participant must be instructed to inform the Investigator about all AEs and these must be documented in the participant records and Case Report Form (CRF) together with their intensity;

- Severe are those AEs which make normal daily routine impossible.
- Moderate AEs impact the normal daily routine
- Mild AEs do not impact normal daily routine.

An AE that is assessed as severe should not be confused with a SAE. Severity is a category utilised for rating the intensity of an event, and both AEs and SAEs can be assessed as severe. An event is defined as 'serious' when it meets one of the pre-defined outcomes as described in Section 6.2.

The Investigator must assign causality to each adverse event in relation to based on the following scale:

CONFIDENTIAL

Page 15 of 21

Cardiology Department, HNELHD
Clinical Trial Protocol: PRESSURE-AF

Version: 1.4
Date: 24/11/2020

- **Not related:** AE for which there is evidence of another explanation, e.g. the adverse event is obviously explained by the participant's disease(s), is in accordance with the known effect of a concomitant medication, or has occurred prior to commencement of ILR follow-up period.
- **Unlikely related:** AE with a time to ILR follow-up commencement that makes a relationship improbable (but not impossible), and disease or other drugs provide plausible explanations.
- **Possibly related:** AE with a reasonable time relationship to ILR follow-up commencement, but which could also be explained by disease or other drugs.
- **Probably related:** AE with reasonable time relationship to ILR follow-up commencement that is unlikely to be attributed to disease or other drugs.
- **Definitely related:** AE with plausible time relationship to ILR follow-up commencement which cannot be explained by disease or other drugs.

All AEs must be documented by the Investigator, regardless of causality.

Expected AEs are defined as all AEs stated in the IB. If an AE has not been previously reported (including type, degree, or frequency) in the IB, it is an unexpected adverse event.

If an AE leads to premature discontinuation of the study, the appropriate pages of the CRF must be completed.

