8.6. SAFETY DATA

8.6.1. Adverse events

AE data will be listed individually and incidence of AEs summarised by system organ class and preferred terms within a system organ class for each treatment group. When calculating the incidence of AEs, each AE, based on preferred terminology defined by Medical Dictionary for Regulatory Activities (MedDRA; Version 13.1, or later), will be counted only once for a given participant. A summary of the number and percent of participants with the following treatment emergent AEs will be displayed by treatment groups:

Cardiology Department, HNELHD
Clinical Trial Protocol: PRESSURE-AF

Version: 1.4
Date: 24/11/2020

- All AEs
- Intervention-related AEs
- Severe AEs
- SAEs
- AEs leading to discontinuation of the study or cross-over.

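### The causality scale in Protocol section 6.1 is timed to an ILR follow-up that this trial does not have and names no exposure, so the by-arm row of intervention-related AEs has no valid definition

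*Protocol*

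**What the plan says.** Section 6.1 makes a causality grade compulsory for every AE and opens the scale with this sentence: "The Investigator must assign causality to each adverse event in relation to based on the following scale". Five grades follow.

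- *Not related* lists as one of its examples that the event "or has occurred prior to commencement of ILR follow-up period".
- *Possibly related* is an "AE with a reasonable time relationship to ILR follow-up commencement, but which could also be explained by disease or other drugs".
- *Probably related* is an "AE with reasonable time relationship to ILR follow-up commencement that is unlikely to be attributed to disease or other drugs".
- *Definitely related* is an "AE with plausible time relationship to ILR follow-up commencement which cannot be explained by disease or other drugs".
- *Unlikely related* uses the same anchor, with a timing that makes a link improbable.

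The section then sets expectedness: "Expected AEs are defined as all AEs stated in the IB".

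Section 8.6.1 uses the causality grade: "A summary of the number and percent of participants with the following treatment emergent AEs will be displayed by treatment groups". Intervention-related AEs are the second of the five items listed there.

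**The concern.** A relatedness grade needs two things: an exposure to judge against and a time at which that exposure begins. The scale supplies neither. Its time reference belongs to something that is not part of this study, and its opening sentence breaks off where the exposure should be named. No grade mentions cardioversion or chest pressure.

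What is at stake is the one safety summary that is meant to separate events attributed to the intervention from the rest, in a trial whose secondary objective is the safety and tolerability of chest pressure. If the grade has no definition, neither has that row.

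**Working it through.** The claim contains no figure, so the check is a comparison of the text.

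1. **Does the anchor exist in this trial?** ILR appears only in the causality scale. It is not in the list of abbreviations, and no device or monitoring period of that name is described elsewhere. The synopsis gives the test strategy as cardioversion with or without chest pressure as the initial approach. Section 2.5 limits participation to the procedure day, and section 6.3 captures AEs from consent to discharge. The anchoring event never happens.

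2. **How many grades depend on it?** *Not*, *Unlikely*, *Possibly*, *Probably* and *Definitely related* all refer to it: 5 of 5. In *Not related* it is only one example beside two others (the participant's disease, a concomitant medication). In the other four it is the timing criterion itself.

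3. **Does the text name the exposure elsewhere in the scale?** No. The lead-in sentence passes straight from the preposition to the scale. The nearest help is the AE definition at the head of section 6.1, which speaks of the study treatment and a strategy, but then of a medicinal product.

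4. **Would the word intervention settle it in section 8.6.1?** Not fully. Both arms receive shocks, and under section 2.7.1 a control participant who reaches the fourth shock also receives chest pressure. An intervention-related event could therefore be one related to cardioversion, which both arms share, or one related to pressure, which most directly distinguishes them. The text does not choose.

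5. **Which outputs use the grade?**

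| Output | Uses causality? |
|---|---|
| All AEs (8.6.1) | No |
| Intervention-related AEs (8.6.1) | Yes |
| Severe AEs (8.6.1) | No |
| SAEs (8.6.1) | No |
| AEs leading to discontinuation or cross-over (8.6.1) | No |
| Chest pain at 30 minutes; shock to proceduralist (4.2) | No |
| 12-month review of AEs (8.1) | No: it refers to adverse events in general |
| SAE reporting (6.4) | No: it sets no relatedness or expectedness condition |

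One of the five summary rows in section 8.6.1 depends on the scale.

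6. **What happens to that row?** There are two outcomes. Read literally, no event can have a reasonable or plausible timing relative to something that never starts, so the three higher grades cannot be met and the row is empty. Read sensibly, each investigator substitutes an anchor (consent, sedation, first shock, first application of pressure) and an exposure (shock or pressure). The trial is described as multi-centre, so these substitutions may differ between sites.

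7. **Expectedness.** The abbreviation list expands IB as Investigator's Brochure. The protocol identifies no such brochure for any part of the treatment. Expectedness does not decide relatedness, and neither section 6.4 nor section 8.6.1 uses it. This is a separate leftover.

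**The case against.** The strongest reply is that the intended meaning is plain. The AE definition mentions the study treatment and a causal relationship with the strategy, section 8.6.1 speaks of the intervention, and an experienced investigator would grade against the procedure. All AEs must be documented whatever their causality, and randomisation protects the between-arm comparison of all AEs, severe AEs and SAEs. On this view the point is a wording slip in one descriptive row.

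Much of that stands. The reach is narrow, and the comparison of overall AE counts is intact. It does not remove the defect, because the general intention does not tell sites which start time to use or whether the shock or the pressure is being judged. Section 6 itself stresses that all staff must know this text.

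A reader might also infer that every same-day event would be graded *Not related*, so that the table is biased towards showing chest pressure as safe. The documents do not support that as an expectation. An event cannot clearly be prior to something that never begins; the timing is simply undefined. That grade also opens by asking for evidence of another explanation. A row empty in both arms would be uninformative, not reassuring.

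**Conclusion.** The point holds as a defect of definition. All five causality grades rest on a time anchor that does not occur in this trial, and the scale states no exposure. The consequence is confined to one of the five AE summary rows in section 8.6.1, which would be empty on a literal reading or inconsistently filled on a practical one. Which of the two would occur, and how far sites would differ, cannot be told from the protocol. The conclusion assumes that no CRF instruction or study manual outside the protocol already supplies the anchor and the exposure.

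Three further inferences are not supported. The recruitment decision at 12 months is not exposed, since section 8.1 acts on adverse events without regard to causality. The brochure reference does not contribute to the relatedness problem. Nor can it be said that nothing is followed after the procedure day: section 6.5 follows AEs until they resolve or stabilise, and only participation and AE capture are short.

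The text should be corrected, at modest priority.

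**What to change.** In section 6.1:

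- Complete the lead-in sentence so that causality is assessed in relation to the study procedure, with two separate entries: relation to the cardioversion shock, and relation to chest pressure. State in section 8.6.1 which of these defines an intervention-related AE, or show both.
- Replace the ILR anchor in all five grades with the start of the study cardioversion procedure, and define that start once.
- In *Not related*, keep onset before that start as an example. AEs are captured from consent, so events before the procedure will be recorded and need a place on the scale.
- Separately, replace the brochure reference with a list of expected events that exists for this trial, or drop the expectedness rule. No stated analysis changes either way.

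The cost is protocol wording and any matching CRF guidance, with ethics approval of the amendment under section 9.3. No sample size, endpoint or efficacy analysis is touched. The change is best made before any AE is graded, since later regrading would have to be done again for each event, possibly with the arm known.
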